Functional status	N/A	Activities of daily living, physical function	Follow-Up VNS Health administrative data
Hospitalization	N/A	A hospitalization to any hospital (for any reason) during the study period	Follow-Up VNS Health administrative data
Quality of Life	Cardiomyopathy Questionnaire (Kansas City) [KCCQ-12]	The Kansas City Cardiomyopathy Questionnaire (KCCQ-12) is a 12-item self-administered questionnaire adapted from the KCCQ, a 23-item self-administered questionnaire which independently evaluates patient's perceptions of their health status with particular focus on heart failure symptoms, impact on physical and social function, the disease's impacts on their quality of life (QOL) within a 2-week recall period.	Interview

Sample Selection/Data Sources: English and Spanish speaking HHAs assigned to care for adults admitted to home care with a primary diagnosis of HF during the study period will be eligible. According to our preliminary estimates, VNS Health HHAs care for 2,280 new HF cases per year, for an estimated 4,560 cases during the 2-year trial. HHAs with less than 1 year of job experience will be excluded. We expect 400 HHAs will need to be screened to reach the goal of 104. Additionally, 12 nurses will be recruited (convenience sampling) to participate in pilot RCT.

HHAs will be studied for 90-days. HHAs will be asked to complete an electronic survey 3 times during the study; first before the virtual orientation session at the time of recruitment (beginning

of the trial; prior to randomization); second after receiving the HF training course; and lastly at 90 days after the completion of the training course.

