
Baseline analyses: For each baseline characteristic in the questionnaire (see attached document), we will examine the distribution and outliers. We will test whether baseline characteristics are balanced between intervention arms using parametric or non-parametric bivariate tests as appropriate. All tests will be conducted at $\alpha=0.05$.

Outcome analyses: Feasibility measures (described above) will be characterized with descriptive statistics (frequencies and proportions) using STATA statistical software. To assess the acceptability of the intervention and trial among study participants, [name] will conduct a series of exit interviews with HHAs and nurses in the trial, as well as with VNS Health staff. The effect of the intervention among HHAs will be assessed for **two primary outcomes:** 1) HF knowledge; 2) HF caregiving self-efficacy and **two secondary outcomes:** 1) intention to leave and 2) job satisfaction (See above Table); alongside other specified outcomes of interest including communication practices (and preventable 911 calls). Finally, the effect of the intervention on two patient outcomes (emergency department [ED] visits; 30-day readmissions; functional status) will be assessed in exploratory analyses. To determine the effect of the intervention on the **primary outcomes**, we will compare HF knowledge and HF caregiving self-

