efficacy scores by trial arm using paired t-tests for normally distributed data or Wilcoxon signed rank test for non-parametric data. We will examine the effect of randomization on the change in scores, using mixed linear regression models. Mixed-effects included a fixed effects categorical variable for time point (baseline/post-course/90 day), an indicator for study arm (control/intervention), a study arm by timepoint interaction and subject-specific random intercept. Primary analyses will be conducted using intention-to-treat, when appropriate. We will examine HHA characteristics across trial arms and adjust for covariates that are imbalanced ($p < 0.10$). We will conduct the same analyses for the secondary outcomes (burnout and job satisfaction). For patient outcomes, we will perform exploratory analyses to determine the effect of the intervention on ED visit rates and hospitalization rates; and functional status, using Poisson mixed effects regression models to account for clustering of patients within HHAs. To measure what would have occurred with usual care (e.g. without enhanced usual care or the intervention), we will assess ED visit rates and 30-day readmission rates among HHAs 90 days before vs. 90 days after randomization, adjusting for clustering of patients within HHAs, and stratified by trial arm. Analyses will be done using STATA statistical software.

Power and Sample Size: To detect minimal clinically important differences (MCID) for both outcomes (a 1-point change in mean score on the Dutch HF Knowledge Scale; an 8-point change in mean score on the HF caregiving self-efficacy), with 80% power, α at 0.05, and conservatively allowing for 15% attrition, we will need 104 HHAs (52 per arm). The overall α at 0.05 enables testing of two hypotheses using Bonferroni's method. Consistent with the goals of this study (to assess feasibility and acceptability of the intervention and obtain preliminary effectiveness estimates on primary outcomes), we have not powered our study on secondary outcomes or on patient outcomes. These calculations were done in Stata v13, College Station, TX.

Statement of the Risks/Benefits for the Study Subjects:

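### Choosing covariates for the primary mixed model by a baseline p<0.10 screen gains almost nothing; use no extra covariates or name them in advance, and make better use of the baseline score (minor)

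*Combined protocol and SAP*

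**What the plan says.** The Outcome analyses section sets out a mixed linear model for knowledge and self-efficacy. It has fixed effects for time point (baseline, post-course, 90 days) and arm, together with "a study arm by timepoint interaction and subject-specific random intercept". The stated target is the effect of arm on change in score.

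The section then adds: "We will examine HHA characteristics across trial arms and adjust for covariates that are imbalanced", with p<0.10 as the trigger. It does not list the characteristics. It does not say whether a flagged one enters as a main effect or crossed with time.

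The Baseline analyses section supplies the tests: "We will test whether baseline characteristics are balanced between intervention arms using parametric or non-parametric bivariate tests as appropriate". It continues "All tests will be conducted at" 0.05.

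The rule carries over beyond the primary outcomes: "We will conduct the same analyses for the secondary outcomes".

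Under Sample Selection/Data Sources, the first survey is placed at the beginning "of the trial; prior to randomization".

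**The concern.** The questionnaire is completed before allocation, so any baseline difference between arms under valid randomisation is chance. A p<0.10 screen therefore flags each characteristic about 10% of the time, whether it is strongly related to the outcome or irrelevant to it. Covariate adjustment in a randomised trial earns its keep through prognosis, and this rule ignores prognosis.

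Two things follow. The primary model cannot be written down until the arms have been compared, and its form is left to the analyst. Also, if a truly prognostic covariate exists, the plan will usually leave it out. What is at stake is some power and some avoidable discretion, not the validity of the trial.

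**Working it through.** **The plan's own figure.** The Power and Sample Size section gives 104 HHAs (52 per arm) for 80% power with 15% attrition. Working back, 44 analysed per arm gives 44/0.85 = 51.8, rounded up to 52. No SD or correlation is stated, so 104 cannot be derived independently. With 44 per arm the detectable standardised effect is (z₁₋α/₂ + 0.842) × √(2/44):
- α = 0.05: 2.802 × 0.2132 = 0.597, implying SDs of 1/0.597 = 1.67 (knowledge) and 8/0.597 = 13.4 (self-efficacy).
- α = 0.025 (Bonferroni, two outcomes): 3.083 × 0.2132 = 0.657, implying SDs of 1.52 and 12.2.

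The checks below use α = 0.025 and effects giving about 80% power. **All correlations and candidate numbers are assumptions**, because the documents give none.

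**Main-effect reading.** With complete data the contrast rests on within-person differences. A term βX that is constant over time cancels from Y(90 days) − Y(baseline), as the random intercept does. In simulation of the planned model with complete data, the SD of the arm-by-time estimate was the same (0.2309) with no covariate, with the screen and with fixed adjustment. With 15% missing at 90 days, power under the rule stayed within 0.1 points of the no-covariate model at every correlation from 0 to 0.5.

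**Covariate crossed with time, planned model.** Setting: random-intercept REML, 52 per arm, 15% missing at 90 days, effect 0.65 SD of change, intraclass correlation 0.5, 20,000 replicates, one candidate. Here r is the covariate's correlation with change.

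| r | No covariate | p<0.10 rule | Fixed | Fixed − rule |
|---|---|---|---|---|
| 0 | 80.8% | 80.7% | 80.4% | −0.3 |
| 0.1 | 80.9% | 80.8% | 80.8% | 0.0 |
| 0.2 | 82.2% | 82.2% | 83.1% | 0.9 |
| 0.3 | 81.8% | 82.2% | 84.0% | 1.8 |
| 0.5 | 83.9% | 85.6% | 91.2% | 5.6 |

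Type I error was 2.5-2.9% under the rule and 2.6-3.1% with no covariate.

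**Change scores compared between arms.** Setting: 44 per arm, effect 0.667 SD, 20,000 replicates.

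| r | No covariate | p<0.10 rule | Fixed | Fixed − rule |
|---|---|---|---|---|
| 0 | 80.2% | 80.1% | 79.8% | −0.3 |
| 0.3 | 79.6% | 80.2% | 83.2% | 3.0 |
| 0.5 | 80.3% | 82.1% | 90.3% | 8.2 |

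At r = 0.5 the rule keeps (82.1 − 80.3)/(90.3 − 80.3) = 18% of the power gain. A longer run (100,000 replicates) gave fixed minus rule of 83.3 − 80.4 = 2.9 and 90.3 − 81.8 = 8.5, with type I error under the rule of 1.9-2.6%. Across the two forms the loss is therefore about 2-3 points at r = 0.3 and 6-9 at r = 0.5.

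**Several candidates.** With ten independent candidates, at least one is flagged by luck in 1 − 0.9¹⁰ = 65% of trials. If flagged covariates are crossed with time, power for rule / no covariates is 79.1 / 81.1% with none prognostic, 80.8 / 81.3% with one at r = 0.3, and 83.6 / 83.7% with one at r = 0.5.

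**Does the unstated form matter?** With one candidate, the main-effect and by-time readings disagree on significance in 4.7% (r = 0) to 24.5% (r = 0.5) of trials in which it is flagged. That is 0.5-2.5% of all trials.

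**Use of the baseline score (a separate matter).** Let ρ be the baseline to 90-day correlation, with the SD of change set to 1. Then σ² = 1/[2(1 − ρ)], and adjusting for baseline leaves variance σ²(1 − ρ²) = (1 + ρ)/2. The unadjusted signal is 0.667/0.2132 = 3.13, giving power Φ(3.13 − 2.24) = 81%. Dividing 3.13 by √[(1 + ρ)/2]:
- ρ = 0.3: 3.13/0.806 = 3.88, power 95%
- ρ = 0.5: 3.13/0.866 = 3.61, power 91%
- ρ = 0.7: 3.13/0.922 = 3.39, power 88%

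Simulating the planned model with baseline means constrained equal gave 94.3 / 90.3 / 87.2%, against 81.9 / 80.7 / 81.3% unconstrained, with type I error of 2.5-2.7%.

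**The case against.** The strongest reply is that the ordinary meaning of adjusting for a covariate is a main effect, and on that reading the rule does no measurable harm. This stands: any loss needs a covariate that predicts change, not merely the level of the score, and that is crossed with time or used in a change-score comparison. The change-score comparison is not the mixed model the plan specifies. Nothing in the documents supports a correlation as high as 0.5, and at 0.2 or below the loss in the planned model is under one point. How much of the gain is lost also depends on the scale: in variance terms the screen keeps about 45% of the gain at r = 0.5, against about a fifth in power.

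The no-covariate column for the planned model is also slightly flattering at r = 0.5. The simulated covariate moves both follow-up scores together, so the random-intercept model understates the standard error by a factor of √(1 − r²/3) = 0.957, and type I error drifts to about 3.1%. The change-score table does not have this problem and shows the same pattern.

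A reader might infer that data-driven selection inflates the false-positive rate. It does not: in these simulations the rule never exceeded the no-covariate model by more than simulation error, and at higher correlations it was conservative.

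A reader might also see a contradiction between the 0.05 level in Baseline analyses and the 0.10 trigger in Outcome analyses. The first sets a level for tests and the second states its own threshold for adjustment. The operative rule is clear, and the difference is at most untidy.

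**Conclusion.** The point holds as a minor one. The screen selects on chance imbalance and leaves the covariate set and its form open until the arms have been compared. It does little or nothing that the model without covariates would not do. Type I error and the validity of the core estimate are not in question.

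The forgone power is conditional: nil on the main-effect reading, and about 2-3 points (r = 0.3) or 6-9 points (r = 0.5) against fixed adjustment if a covariate predicts change and can act on the arm-by-time contrast. The stronger reading, that the plan throws away a substantial gain in power, is not supported, because the documents give no correlations, number of candidates or covariate form.

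The larger figures for baseline handling show what a better use of data already collected could bring. They are not a measure of the screen's harm and do not raise the severity.

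**What to change.** - Delete the p<0.10 rule and the baseline significance tests, and report baseline characteristics by arm descriptively. The 0.05 / 0.10 difference then disappears.
- Before outcomes are examined by arm, choose one of two options: no extra covariates, or two or three named, recorded covariates judged prognostic. Include named covariates whatever their balance and with covariate-by-time terms. Language ("English and Spanish speaking HHAs assigned to care for adults") and experience ("HHAs with less than 1 year of job experience will be excluded") appear only as eligibility criteria, so they are candidates only if they are recorded. The documents do not show that they are prognostic.
- State how the baseline score is used: either constrain baseline means to be equal across arms, or adjust the two follow-up scores for baseline.
- Keep the model without extra covariates as a sensitivity analysis, and apply the same list to the secondary outcomes.
- State whether outcomes have already been seen by arm. The document is dated 4/22/2025, the recruitment script gives an event on 1/24/23, and the study is to run 24 months, so this is possible. If they have been seen, report the analysis as planned, including its rule, alongside the model without covariates. Label every departure as post hoc, including dropping the rule.

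**Cost.** Wording only, with no new data. Each covariate with time terms adds three coefficients, so two or three add 6 to 9 in a model with about 104 × 3 − 0.15 × 104 = 296 rows. Each useless covariate crossed with time costs about 0.4 power points (80.8% to 80.4%), so using none is a sound choice if none is thought prognostic.

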An overview of the pilot RCT and the randomization scheme is shown in the Figure below. After being consented, all HHAs will attend a virtual orientation session and virtual HF training course. Prior to the course, all HHAs will complete a baseline questionnaire (see attached survey document) and be randomized in a 1:1 ratio (T1). The training course will be conducted via Zoom and led by WCM investigators and VNS Health staff members. After taking the course, HHAs in both arms will take a short post-course questionnaire (to assess the two primary outcomes; knowledge and HF caregiving self-efficacy). HHAs randomized to the enhanced usual care arm will receive a just-in-time course refresher via their Care Connect app (self-driven educational content) prior to caring for their HF patient. HHAs randomized to the intervention will receive a just-in-time course refresher as well as an app training session from a Weill Cornell Medicine research assistant (overseen by [name] in computer science). HHAs in this arm will be encouraged to use the app when they have questions about their patient, want to access HF-related content, or need to communicate with the nurse. To reinforce their use of the use of the application chat features, they will receive "do not reply" text based notifications reminding them that the feature is there and can be used. Following the care of their first patient, HHAs in both arms will take a follow-up questionnaire. Each HHA will be involved in the study for 90 days. During that time, if the HHA is assigned to a new HF patient, they can continue participation although they will remain randomized to their original treatment arm to avoid contamination. De-identified data on HF patients cared for by the HHAs (demographics, clinical conditions, ED visits; 30-day/90-day readmissions; hospitalization; functional status; and quality of life) will be retrospectively collected by the VNS Health from intake/referral data and OASIS. HHAs will receive \$100 for participating; they will receive \$25 at trial start, \$25 following the completion of the heart failure training course and survey 2, \$25 following the 45-day (mid-study) interview, and \$25 following the final survey.

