Data to be Collected and Analyzed: The questionnaire (see attached document) will be administered using Research Electronic Data Capture (REDCap), a web-based, secure, data storage program at Weill Cornell Medicine at several time points during the study. A research assistant at Weill Cornell Medicine will export the de-identified data that is collected in REDCap to STATA, a statistical software package, for analysis. A data analyst at Weill Cornell Medicine will analyze this data under PI [name]'s supervision (IRB at WCM to safeguard this aspect of the project). App usage data from the mHealth app (intervention arm) will be monitored by [name] (Scientific adviser/collaborator from Cornell; health technology). After 90 days, data from the mHealth app will be extracted by [name] and the Care Connect team (that works with Partner's in Care) and transferred and stored on a secure server on a password-protected computer at Weill Cornell Medicine which is monitored by WCM ITS. This data will be analyzed by a data analyst at Weill Cornell under PI [name]'s supervision. Finally, data on the HF patients cared for by the HHAs in the trial (demographics, clinical co-morbidities, and outcomes [ED visits and 30-day readmissions, functional status]) will be extracted by the VNS Health programmer from the agency's clinical records and administrative data. This type of data collection is part of the agency's ongoing quality improvement activities and falls under the agency's routine admissions procedures with patients. Like many studies at VNS Health, the clinical outcomes will be extracted from the Home Health Outcome and Assessment Information Set (OASIS). Data will be de-identified and analyzed at VNS Health, under Site-PI [name] supervision. All OASIS data will be analyzed at VNS Health. At the end of the study, under [name] supervision, trial participants (HHAs, nurses) will be interviewed to assess their experience with the training course and mHealth app. Additionally, short, telephone-based interviews will be conducted with a sub-set of patients by [name]. These interviews will focus on their perspectives towards their HHAs, not about their medical care or their health, and will not last more than 30 minutes. They will be audio-recorded and professionally transcribed. Transcripts will be stored on a secure password-protected computer at WCM, which is monitored by WCM ITS. [name] will oversee the qualitative data analysis.

Brief Overview of Analytic Methods:

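### Functional status, an undefined score, is put under the Poisson event-rate model with no start-of-care adjustment; for a short or low-variance score the standard error would be about 1.3 to 1.6 times too large

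*Combined protocol and SAP*

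**What the plan says.** **Model.** In Brief Overview of Analytic Methods, Outcome analyses, the patient outcomes share one sentence: "ED visit rates and hospitalization rates; and functional status, using Poisson mixed effects regression models to account for clustering of patients within HHAs". No other model is named for functional status and no baseline value enters. The covariate adjustment in that paragraph concerns characteristics of the home health aides (HHAs), not of patients. The aides' own scale scores, by contrast, get a linear mixed model in which baseline is one of the time points.

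**Definition.** In Table 1 the scale column for functional status reads N/A, the whole description is "Activities of daily living, physical function", and the source is "Follow-Up VNS Health administrative data". No items, range, scoring direction or assessment time appear there or elsewhere. The aide outcomes in the same table list both baseline and follow-up questionnaires.

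**Source elsewhere.** Study Design says that patient data, with functional status in the list, "will be retrospectively collected by the VNS Health from intake/referral data and OASIS". Data to be Collected and Analyzed names OASIS as the source of the clinical outcomes and says that this collection "falls under the agency's routine admissions procedures with patients".

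**Standing.** Patient outcomes are exploratory, and Power and Sample Size states that "we have not powered our study on secondary outcomes or on patient outcomes".

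**The concern.** A Poisson model suits ED visits and hospitalizations, which are events over a period. A functional rating is a level at a point in time. Even if it were scored as the number of activities in which the patient is dependent, that would be a bounded count and not events per unit of time, so a rate ratio would be hard to interpret.

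The practical problem is the variance. The aide random intercept lets the marginal variance rise above the Poisson level, but nothing in the model lets it fall below. A score on a short scale can easily vary less than its mean implies. The standard error is then too large and a real difference is more likely to be missed.

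The second issue is the unused starting value. If function at start of care is in the OASIS extract, leaving it out gives away precision in a small trial. Table 1 points only to follow-up, while two other sections point to data collected at intake.

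**Working it through.** **Plan's own figure.** There is none for this outcome. The 104 aides (52 per arm) were sized on the two primary outcomes and do not bear on functional status.

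**Inputs.** From the documents: 52 aides per arm, 1:1 allocation, Poisson model with clustering by aide. Assumed, because the documents give no scale: the means, SDs and ranges below, an aide intraclass correlation of 0.05, and 1 or 2 patients per aide.

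**Step 1, low-variance scores.** When the variance is below the mean, the intercept variance is estimated near zero and the planned model behaves like a plain Poisson model. Then model SE / true SE = sqrt(mean)/SD, and the true two-sided error is 2 x P(Z > 1.96 x ratio).
- 0-3 item, mean 1.5, SD 0.8: sqrt(1.5)/0.8 = 1.53; 1.96 x 1.53 = 3.00; error 0.3%.
- Mean 8, SD 2: sqrt(8)/2 = 1.41; 1.96 x 1.41 = 2.77; error 0.6%.
- 0-6 score, mean 3, SD 1.5: sqrt(3)/1.5 = 1.15; 1.96 x 1.15 = 2.26; error 2.4%.

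**Step 2, the planned model in simulation.** When the variance exceeds the mean, the formula no longer applies, because the intercept absorbs excess. So a Poisson random-intercept model was fitted to simulated trials with no true effect. Ranges cover all runs with 1 and 2 patients per aide.

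| Assumed score | Model SE / true SE | False-positive rate (nominal 5%) |
|---|---|---|
| 0-3 item, mean 1.5, SD 0.8 | 1.37 to 1.60 | 0 to 1.3% |
| Mean 8, SD 2 | 1.32 to 1.45 | 0 to 1.6% |
| 0-6, mean 3, SD 1.5 | 1.15 to 1.18 | 2.3 to 2.7% |
| Mean 8, SD 4 or 5 | 0.96 to 1.06 | 4.4 to 6.7% |
| 0-30, mean 15, SD 5 | 1.01 to 1.02 | 3.7 to 4.0% |
| 0-100, mean 50, SD 20 | 0.85 to 0.93 | 6.7 to 10.0% |

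The estimated ratio of means stayed between 0.99 and 1.01. With 300 runs, the Monte Carlo standard error of a 5% rate is sqrt(0.05 x 0.95/300) = 1.3 percentage points, so the middle rows are indistinguishable from nominal.

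**Step 3, what the over-wide SE costs.** Take an effect that a correctly sized test would detect with 80% power, so its expected z is 1.96 + 0.84 = 2.80. With the SE inflated by r, power is P(Z > 1.96r - 2.80): 60% at r = 1.3, 51% at r = 1.41 and 37% at r = 1.6.

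**Step 4, the starting value.** Adjustment multiplies residual variance by 1 - rho^2. With rho assumed at 0.5 to 0.7 this is 0.75 to 0.51, a cut of 25% to 49%. In simulation at rho 0.6, a baseline-adjusted linear model with cluster-robust SE had false-positive rates of 3.8% to 5.8%. Its SE was about 14% to 19% smaller than without the baseline value; the formula gives 1 - sqrt(0.64) = 20%.

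**The case against.** The best defence is that the model is a mixed model. A reader might apply the plain Poisson formula to wide scores and infer serious false-positive inflation: with mean 8, SD 4 gives a ratio of 0.71 and an error of 17%, and SD 5 gives 0.57 and 27%. Those figures describe a model without the random intercept. Under the planned model the same cases come back to 4.4% to 6.7%. This part of the defence stands.

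Three other strong readings also fail:
- **The effect estimate would be wrong.** With a log link the coefficient is a ratio of means, and it showed no material bias.
- **The comparison would be dominated by how disabled patients were at admission.** Patients may join an aide after the aide is randomised, so comparability at admission is not guaranteed by design. But no section ties patient assignment to arm, and at the assumed correlations admission status explains 25% to 49% of variance. The main loss is precision.
- **Function is collected only at follow-up.** That is Table 1's label; Study Design names intake data and OASIS.

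It can also be said that an undefined measure cannot be shown not to be a count, and that the semicolon in the analysis sentence might confine Poisson to the two rates. On that second reading functional status has no model at all, so a correction is needed either way. Finally, the outcome is exploratory and unpowered, which limits the consequences but does not supply a definition.

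**Conclusion.** The point holds in limited form. The only model named for functional status is built for event rates, and whether its standard error is right depends on a scale that the plan never states. For a short or low-variance score the SE is about 1.3 to 1.6 times too large and the true error about 0-2% instead of 5%, so the failure is conservative and costs power. For the wider scores tried the SE is about right, except that a 0-100 score may have one up to about 15% too small. Bias in the ratio of means is not supported.

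All sizes rest on assumed means, SDs, intraclass correlation and 1 or 2 patients per aide. The gain from adjustment rests on an assumed correlation and on the start-of-care score being in the OASIS extract, which the documents suggest but do not state. No primary outcome, sample size or decision depends on this analysis, so the change is worthwhile but not critical.

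**What to change.** - **Analysis sentence:** take functional status out of the Poisson sentence and keep that model for ED visits and hospitalizations. Analyse the follow-up score with a linear mixed model (ordinal for a short scale), with an aide random intercept and the start-of-care score as covariate. If that score proves not to be available, say so and drop the covariate; the change of model still stands.
- **Table 1:** define functional status as a named OASIS activities-of-daily-living score, with items, range, direction and assessment times.
- **Source:** reconcile Table 1's follow-up source with the intake, referral and OASIS data in Study Design and in Data to be Collected and Analyzed.

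The cost is one table row, one sentence and one more field in the VNS Health extract.
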